9.2.11.2 Visual Analog Scale

A descriptive summary will be provided for the VAS values, change from Baseline and percentage change from Baseline using 8-number summary by visit and treatment group.

Change from Baseline and percentage change from Baseline by visit, with the week 12 being the primary visit of interest, will be analyzed using an ANCOVA model with treatment as fixed effect and the associated baseline value as covariate. Least squares means and standard errors will be presented for each visit, p-value and 2-sided 95% confidence interval for treatment differences will be presented for each visit. Significance tests will be based on least-squares means using a two-sided $\alpha = 0.05$.

By-subject listing will be provided for observed and derived variables.

Mean \pm SD and change from baseline for 5D-Itch Scale Total Score and VAS values by visit and treatment group will be plotted.

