***Safety Follow-up and Early Termination Visit:*** The safety follow-up visit (or End of Study [EOS] visit) will occur 4 weeks after the last dose of study drug for all subjects, including those who discontinue treatment early (ie, prior to completing 12 weeks of dosing). Final study assessments will be completed at that visit.

Subjects who discontinue treatment early should return to the clinic as soon as possible following the last dose of study drug for an EOT visit. They should then return for the EOS visit 4 weeks following last dose of study drug.

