EDP-305 was generally well tolerated at single doses up to 80 mg and at multiple doses up to 20 mg for 14 days. TEAEs occurring in  $\geq 2$  EDP-305 treated subjects in MAD were: headache and pruritus in HV, and constipation and pruritus in PN. No SAEs or Grade 4 AEs were reported. Drug related pruritus was reported after multiple dosing at the higher doses of EDP-305 10 mg (n=2) and 20 mg (n=7), and PBO (n=1), with 1 discontinuation at 20 mg in HV (moderate). Majority of drug related pruritus were mild to moderate (except one subject with severe). No pruritus was observed at lower doses (below 10 mg). No clinically significant laboratories were reported except one transient Grade 2 ALT/AST elevation in one subject (MAD-HV-20 mg) that led to drug discontinuation. Total, LDL-, HDL- cholesterol and triglycerides did not differ between EDP-305 and placebo in either healthy or PN subjects at any dose, except at 20 mg in PN for cholesterol and HDL.

A dose proportional increase in exposure was observed following single and multiple doses of EDP-305. Pharmacokinetic (PK) profiles following single doses of EDP-305, indicated linear, one-compartment PK, with monophasic decline. Half-life was similar following single doses with a mean ranging from 11 to 16 hours. A high fat meal increased EDP-305 exposure by approximately 200%. Half-life ranged from 10-23 hours following multiple doses of EDP-305. There was more drug accumulation (~3-fold) observed following 20 mg dose compared to lower doses. Similar exposures were observed in both HV and PN subjects. The metabolite (EP-022571, EP-022572 and EP-022679) levels were generally low (<5% of parent drug), following single and multiple doses of EDP-305. EDP-305 and metabolite levels in the urine were low and

[REDACTED]

[REDACTED]

[REDACTED]

[REDACTED]

[REDACTED]

[REDACTED]

			[REDACTED]		[REDACTED]		
[REDACTED]	[REDACTED]	[REDACTED]	[REDACTED]	[REDACTED]	[REDACTED]	[REDACTED]	[REDACTED]
[REDACTED]	[REDACTED]	[REDACTED]	[REDACTED]	[REDACTED]	[REDACTED]	[REDACTED]	[REDACTED]
[REDACTED]	[REDACTED]	[REDACTED]	[REDACTED]	[REDACTED]	[REDACTED]	[REDACTED]	[REDACTED]
[REDACTED]	[REDACTED]	[REDACTED]	[REDACTED]	[REDACTED]	[REDACTED]	[REDACTED]	[REDACTED]
[REDACTED]	[REDACTED]	[REDACTED]	[REDACTED]	[REDACTED]	[REDACTED]	[REDACTED]	[REDACTED]
[REDACTED]	[REDACTED]	[REDACTED]	[REDACTED]	[REDACTED]	[REDACTED]	[REDACTED]	[REDACTED]
[REDACTED]	[REDACTED]	[REDACTED]	[REDACTED]	[REDACTED]	[REDACTED]	[REDACTED]	[REDACTED]

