8.3 Prior and Concomitant Medications

Subjects taking UDCA at the start of the study must remain on the same dose of UDCA throughout the 12-week dosing period. Subjects who were not taking UDCA at the start of the study will not be allowed to initiate treatment during the study. Subjects will be classified as taking or not taking UDCA.

Medications will be categorized by medication group and subgroup according to WHODRUG (Version Global B3 2017SEP01 DDE+HD (Enhanced + Herbals)). Refer to the Coding Conventions document for this study.

A medication will be considered concomitant if started or continued to be taken after first dose of study drug through 30 days after the last dose of study drug. Otherwise if a medication was stopped prior to first dose of study drug then it will be considered prior.

Prohibited medications are inhibitors and inducers of CYP3A4 and P-gp (taken between 14 days prior to first dose through 30 days after last dose of study drug). Any medication that inhibits or induces the transporter proteins P-gp are also prohibited during the study. Use of a new statin regimen is prohibited from Screening and throughout study duration. Additional details of prohibited medications please see protocol section 5.9. For protocol restrictions other than prohibited medications, please see the protocol section 5.10

In order to flag prohibited medications taken in the study, each medication taken will be compared against a pre-specified list of all prohibited medications. Prior, Concomitant and Prohibited medications will be summarized based on the number and percentage of subjects using each medication along with the number and percentage of subjects using at least one medication within each medication group and subgroup.

Prior, concomitant, and prohibited medications will be summarized for the Safety Population. All medications will be listed per subject.

9 Efficacy Analysis

The variables from the data to be used to produce the analysis of the objectives and corresponding endpoints are presented below. All efficacy endpoints will be evaluated using the Full Efficacy population.

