9.1 Primary Endpoint

9.1.1 Definition of Primary Endpoint

The primary endpoint is defined as the proportion of subjects who have either a 20% reduction in ALP from pre-treatment values or normalization of ALP at Week 12. All subjects in the Full Efficacy population will be included in the analysis of the primary endpoint. Meeting either of these conditions will be considered meeting the primary endpoint of ALP response. Subjects who are missing either Baseline or Week 12 ALP results cannot have either condition evaluated, and will therefore be counted as failure (non-responder). Subjects having both Baseline and Week 12 ALP results will each be evaluated as follows:

1. Percent change will be calculated as $[(ALP \text{ at Week 12} - ALP \text{ at Baseline}) / ALP \text{ at Baseline}] * 100$. The subject will be considered to have successfully achieved 20% reduction in ALP if the result is ≤ -20 .
2. The subject will be considered to have successfully achieved ALP normalization if ALP was abnormal at baseline and normal at week 12.

If either condition is met, the subject is a responder (ALP Response = YES); if the subject fails both conditions, the subject is a non-responder (ALP Response = NO). The proportion of subjects with a 'Yes' for ALP Response will be compared among the 3 study treatment groups. The denominator for this calculation is the number of subjects in the Full Efficacy population.

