9.1.3 Imputation of Missing Data

To account for missing data, a sensitivity analysis will be performed using the multiple imputation Markov Chain method.

MMRM Using Multiple imputation (MI)

To assess robustness of the efficacy analysis, sensitivity analysis with missing values imputed by MI will be performed on ALP change from baseline data. In the first stage, missing values will be imputed by Markov Chain Monte Carlo (SAS PROC MI, MCMC) to make the missing pattern monotone (by filling in

imputed values of ALP between 2 non-missing values). In the second stage, monotone linear regression will fill in missing values through Week 12. SAS PROC MI and PROC MIXED will be used to obtain MMRM estimates of treatment difference. SAS PROC MIANALYZE will be used to combine estimates and to generate the average test statistics for hypothesis testing. The Missing at Random method will be used with the following parameters MAR – assume missing at random, number of imputation=100, seed=SEED11 (for MCMC) and SEED12 (for MONOTONE REG) for imputation.

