9.2.11 Pruritis

9.2.11.1 5D-Itch Scale

The 5-D questionnaire (Elman 2010) is a specific tool used to quantify the magnitude of pruritus in PBC (and other diseases). It consists of 5 domains: duration, degree, direction, disability, distribution, as well as the total score. Each of the domains and the total score will be summarized by visit and treatment, with the week 12 visit being considered as the primary visit of interest.

The disability domain will be the highest score obtained from the daily activities of sleep, leisure/social activities, housework/errands, and work/school. The disability domain will only be calculated if at least 3 daily activities are documented.

The distribution domain includes 16 locations of itch and is categorized to a scale of 0 to 5, based on the sum of the number of affected locations: sum of 0 to 2 = score of 1, sum of 3 to 5 = score of 2, sum of 6 to 10 = score of 3, sum of 11 to 13 = score of 4, sum of 14 to 16 = score of 5.

The total 5D score is obtained by summing up the domain scores and ranges between 5 (no pruritus) and 25 (most severe pruritus). The total score will not be calculated if any of the domain scores is missing.

For each of the domains and the total score, the value at each visit, the change from Baseline and percentage change from Baseline will be summarized for each of the domains. Statistical inference will be tested using an ANCOVA model with treatment as fixed effect and the associated baseline value as covariate. Least squares means and standard errors will be presented for each visit, p-value and 2-sided 95% confidence interval for treatment differences will be presented for each visit. Significance tests will be based on least-squares means using a two-sided $\alpha = 0.05$.

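### The Week 12 itch ANCOVA has no rule for subjects who stop early, so it is in effect an observed-case comparison and may understate drug-related itch

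*SAP*

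**What the plan says.** Change from Baseline in the 5-D itch scale and the VAS at Week 12 is a secondary endpoint (Protocol 2.2.2). SAP 9.2.11.1 summarises the 5-D domains and total by visit, "with the week 12 visit being considered as the primary visit of interest". SAP 9.2.11.2 gives the VAS analysis as "Change from Baseline and percentage change from Baseline by visit, with the week 12 being the primary visit of interest". Both use an ANCOVA with treatment and baseline, and report LS means, p-values and confidence intervals at each visit. On the population, the opening of SAP Section 9 says: "All efficacy endpoints will be evaluated using the Full Efficacy population".

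Rules for missing data:
- **5-D itch:** within a questionnaire only: "The total score will not be calculated if any of the domain scores is missing". Nothing covers a missed visit.
- **VAS:** none.
- **ALP:** SAP 9.1.1 says "Subjects who are missing either Baseline or Week 12 ALP results cannot have either condition evaluated" and counts those subjects as non-responders. SAP 9.1.3 adds a "sensitivity analysis with missing values imputed by MI will be performed on ALP change from baseline data".

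The SAP 6.3 windows are Days 4-21 for Week 2, 22-42 for Week 4, 43-70 for Week 8, and Day 71 to seven days after end of treatment for Week 12. Follow-up starts after those seven days. Where several values share a window, the one nearest the target day is used.

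For early stoppers the Protocol synopsis says: "Subjects who discontinue treatment early should return to the clinic as soon as possible following the last dose of study drug for an EOT visit". The End of Study (EOS) visit follows four weeks after the last dose. The Schedule of Assessments lists both itch scales at Day 1, Weeks 4 and 8, EOT/Week 12 and EOS.

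**The concern.** An ANCOVA at one visit can use only subjects who have a value at that visit. Naming the Full Efficacy population does not supply the missing scores. If some subjects stop because of itch, their absence depends on the outcome being measured, and those who remain at Week 12 are the ones who tolerated the drug.

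Pruritus is a secondary objective, and Protocol 4.2.2 justifies the two doses partly by a low chance of causing it. In Phase 1, drug-related pruritus occurred at 10 mg (two subjects), 20 mg (seven) and placebo (one), with one discontinuation at 20 mg (Protocol 1.4.1). A Week 12 comparison that loses itch-driven stops would lean toward tolerability, and more so in whichever arm has more of them. The early stoppers' EOT scores are collected, so most of the lost information is already in the database.

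**Working it through.** **1. The plan's own dropout figure.** The documents state no figure for the itch comparison. The only related one is enrolment for 10% discontinuation: 105 / 0.9 = 116.7, so 117. The next multiple of 7 for 3:3:1 is 119, or 51:51:17, which matches the stated 119. If the 10% applies equally across arms, 0.10 x 51 = 5.1, about five subjects per active arm stopping for any reason.

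**2. Where an early stopper's itch scores land.** This applies the SAP 6.3 windows as written and reads end of treatment as the day of last dose.

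| Last dose | EOT visit same day | EOT visit 7 days later | EOS visit (+28 days) |
|---|---|---|---|
| Day 14 | Week 2 | Week 2 | Day 42: Week 4 range and follow-up |
| Day 30 | Week 4 | Week 4 | Day 58: Week 8 range and follow-up |
| Day 40 | Week 4 | Week 8 | Day 68: Week 8 range and follow-up |
| Day 60 | Week 8 | Week 8 | Day 88: follow-up |
| Day 64 | Week 8 | Week 12 | Day 92: follow-up |
| Day 71 | Week 12 | Week 12 | Day 99: follow-up |

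Three results follow.
- A stop before Day 64 leaves no Week 12 itch score (64 + 7 = 71). A stop on Days 64-70 gives one only if the EOT visit is on Day 71 or later and within seven days.
- An EOT visit on Days 4-21 falls in Week 2, where no itch assessment is scheduled.
- For stops up to Day 42 (42 + 28 = 70) the off-drug EOS score also lies in the Week 4 or Week 8 range, and no precedence is given. With a last dose on Day 40, an EOT visit on Day 43 is 13 days from the Week 8 target of Day 56, while EOS on Day 68 is 12 days away. The nearest-value rule would pick the off-drug score.

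**3. Size at Week 12.** Let d be the share of an active arm that stops for itch, and G the excess itch of stoppers over completers. The mean over all subjects is (1 - d) x completers + d x stoppers = completers + d x G. The observed mean is therefore low by d x G. The documents give neither d nor G, so all values below are assumed, with no itch-driven stops on placebo.

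| d | G = 0.5 SD | G = 1 SD | G = 2 SD |
|---|---|---|---|
| 5% | 0.025 SD | 0.05 SD | 0.10 SD |
| 10% | 0.05 SD | 0.10 SD | 0.20 SD |
| 20% | 0.10 SD | 0.20 SD | 0.40 SD |

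As a fraction of the scale, 5-15% stopping with an excess of 30-50% of the scale gives 0.05 x 30 = 1.5% to 0.15 x 50 = 7.5%. If G = 0, or if placebo stops balance the active ones, the understatement is zero.

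**4. Effect on detecting an itch difference.** Power = Φ(Δ / √(1/n1 + 1/n2) - 1.96), with Δ in SD units. For an assumed true difference of 0.8 SD and 51 v 17 subjects, power is 81.5%. With 10% missing and a 1 SD gap (Δ = 0.7, 45.9 v 17) it is 69.3%. With 20% and 2 SD (Δ = 0.4, 40.8 v 17) it is 28.3%.

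**The case against.** The case against has several parts.

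- **Nothing says observed-case.** True: it is inferred from silence. But a single-visit ANCOVA without an imputation rule has no other default.
- **The windows may not govern the itch scales.** SAP 6.3 computes relative day for laboratory, vital-sign, ECG and PD data and does not name questionnaires. The Schedule of Assessments puts EOT and Week 12 in one column. If itch scores were mapped by nominal visit, an early EOT score would enter Week 12 and most of the problem would disappear. However, SAP 6.3 introduces its table as covering all visits, so windowing is the more natural reading. The ambiguity itself needs resolving.
- **The subjects are not lost.** A reader might infer that itch-driven stoppers are excluded from the itch analysis altogether. They are not. EOT scores on Days 22-70 can enter the Week 4 or Week 8 comparisons, which carry p-values and intervals, and later ones can count at Week 12. SAP 10.1 tabulates TEAEs by preferred term and grade, and those leading to discontinuation. This stands, but Protocol 11.6.1 rules out testing of adverse events, so those tables do not compare itch severity between arms.
- **Little itch is expected.** Phase 1 saw no pruritus below 10 mg. The trial doses are put at about 2.5 and 5 mg of the Phase 1 suspension (Protocol 4.2.2), and exclusion criterion 16 removes subjects with a history of severe, systemically treated pruritus. This makes itch-driven stopping less certain. It does not rule it out, because Phase 1 dosed for 14 days in subjects without PBC.
- **A worst-value endpoint would be no better.** It would replace the protocol's Week 12 endpoint, and a maximum depends on how often itch is scored. Early stoppers have fewer scheduled scores, while Protocol 10.3 adds scores at any visit where itch is reported. This stands, so worst value belongs in a supporting role.
- **Other secondary ANCOVAs share the gap.** Also true. Itch differs because the measured outcome is itself a plausible reason for stopping.

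**Conclusion.** The gap is real and moderate in importance. Under the SAP 6.3 windows, subjects who stop before about Day 64 have no Week 12 itch score and no rule brings them in. The Week 12 VAS and 5-D comparisons may therefore understate drug-related itch if subjects stop because of pruritus. The size is d x G and is unknown. At the planned all-cause rate of 10%, and supposing every stop is for itch with a 1 SD excess, it is 0.10 SD. It can be zero. The 15% and 20% rates shown exceed the planned all-cause rate and are outer cases.

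A reader might go further and infer that a known class effect is being hidden, or that itch will be understated. The documents support neither. They report pruritus for this drug at 10 and 20 mg and none below 10 mg, state no class effect, and give no rate of stopping for itch. The conclusion rests on two readings: that the windows apply to the itch questionnaires, and that the ANCOVA uses available values only. The primary ALP endpoint is unaffected.

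**What to change.** Keep the protocol's Week 12 change from Baseline as the itch endpoint, and before unblinding add the following to SAP 9.2.11 and 6.3:

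1. A prespecified sensitivity ANCOVA for VAS and 5-D total in the Full Efficacy population. Use the Week 12 score where there is one, and otherwise the last on-treatment score, including the early EOT visit.
2. Change from Baseline to the worst on-treatment score as a further supportive analysis.
3. A statement that the SAP 6.3 windows apply to the itch questionnaires.
4. A statement that an EOS (off-drug) score never fills an on-treatment visit window.

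The cost is a few derived variables and tables from data already collected. There are two limits to state. An early EOT score may be taken shortly after the last dose, when itch may already be easing, so say how long after the last dose it still counts (SAP 6.3 and 10.1 already use seven days). A worst value depends on the number of assessments, so report that number by arm beside it.

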9.2.12 Quality of Life

9.2.12.1 PBC-40

PBC-40 Quality of Life questionnaire for this study does not collect an overall score. The 40 questions from the PBC-40 questionnaire will be scored from 1-5, with 5 representing the highest impact and 1 the lowest impact of PBC on the quality of life. The direction is reversed to reflect this impact. There will be 6 domains computed from the 40 questions in the following manner:

- 1.) Symptoms: Sum of questions 1-7. Question 1 will be scored with 'Never'=5 to 'Always'=1. The remaining questions will be scored with 'Never'=1 to 'Always'=5. If 4 or more of the 7 questions are missing, then the domain will be left as missing. If 4 or more questions are answered, any missing answered will be imputed using the median value of the non-missing questions used for this domain. The range of possible scores for this domain are [7,35].
- 2.) Itch: Sum of questions 8-10. All 3 questions will be scored with 'Never'=1 to 'Always'=5 and 'Did not apply/no itch'=0. If 2 or more of the questions are missing, then the domain will be left as missing, otherwise, all missing values will be imputed using the median of the other non-missing values used in this question. The possible range of scores for this domain are [0,15].
- 3.) Fatigue: Sum of questions 11-21. All questions will be scored as 'Never'=1 to 'Always'=5. If 6 or more of the 11 questions are missing, then the domain will be left as missing. If 6 or more questions are answered, any missing answered will be imputed using the median value of the non-missing questions used for this domain. The range of possible scores for this domain are [11,55].
- 4.) Cognition: Sum of questions 22-27. All questions will be scored as 'Never'=1 to 'Always'=5. If 4 or more of the 6 questions are missing, then the domain will be left as missing. If 4 or more questions are answered, any missing answered will be imputed using the median value of the non-missing questions used for this domain. The range of possible scores for this domain are [6,30].
- 5.) Social: Sum of questions 29, 31, 32, 34, 35, 36, 37, 38, 39, and 40. Questions 29, 31 and 32 will be scored from 'Not at all'=1 to 'Very Much'=5. Questions 29 and 31 will also include 'Does not apply'=0. The remaining questions will be scored from 'Strongly agree'=5 to 'Strongly disagree'=1. If 6 or more of the 10 questions are missing, then the domain will be left as missing. If 6 or more questions are answered, any missing answered will be imputed using the median value of the non-missing questions used for this domain. The range of possible scores for this domain are [8,50].
- 6.) Emotional: Sum of questions 28, 30, and 33. Questions 28 and 30 will be scored from 'Not at all'=1 to 'Very Much'=5 and 'Does not apply'=0. The remaining question will be scored from 'Strongly agree'=5 to 'Strongly disagree'=1. If 2 or more of the 3 questions are missing, then the domain will be left as missing. If 2 or more questions are answered, any missing answered will be imputed using the median value of the non-missing questions used for this domain. The range of possible scores for this domain are [1, 15].

A descriptive summary will be provided for the domains, the change from Baseline and percentage change from Baseline for each domain, using 8-number summary by visit and treatment group.

Change from Baseline and percentage change from Baseline by visit, with the week 12 being the primary visit of interest, will be analyzed using an ANCOVA model with treatment as fixed effect and the associated baseline value as covariate. Least squares means and standard errors will be presented for each visit, p-value and 2-sided 95% confidence interval for treatment differences will be presented for each visit. Significance tests will be based on least-squares means using a two-sided $\alpha = 0.05$.

By-subject listing will be provided for observed and derived variables.

